Assuming a minimum of 4 screws per patient, the estimated probability of at least one non-clinically acceptable screw is 12% in the robotic group and 25% in the navigated and free hand group.

Using a two-sided alpha of 0.05, 80% power, and a 1:6 group ratio, the required sample size is 71 patients in the robotic-assisted surgery group and 426 patients in the non-robotic-assisted surgery group, for a total of 497 patients. We added patients to 75 in the robotic-assisted surgery group, for a total of 501 patients, to be able to include an equal number of patients from Örebro, Umeå and Uppsala. This estimate is conservative, as most patients are expected to receive more than 4 screws, which would increase the likelihood of detecting placement differences.

The primary analysis will use either mixed-effects logistic regression or logistic regression with cluster-robust standard errors to account for intra-patient correlation of screw outcomes.

A secondary analysis of robot-assisted surgeries after the first 501 patients may be performed.

Substudy 2 - Primary outcome - Learning curve (surgical time)

To evaluate the learning curve associated with robotic-assisted surgery, we will model operative time as a function of case number. Operative time is expected to decrease with experience, then plateau. We will use mixed-effects piece-wise linear regression with the surgeon as a random effect to estimate the case number at which operative time levels off. We will look both at wheel-in wheel-out time (primary), and skin-to-skin time (secondary). We expect to do this analysis after each center has performed 100 robot-assisted spine surgeries, in total 300 surgeries.

We have not conducted a traditional power analysis for this substudy, as the objective is not to test a binary hypothesis but to estimate when operative time stabilizes. If no clear inflection point is observed, this will be interpreted as evidence that the learning curve is either very short (already completed), very gradual, or inconsistent. Such a result would itself be informative, and will require us to compare operative times with today's standard of care, navigated or free hand surgery.

Substudy 3- Primary outcome – Reoperation rate at 2 years

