The primary outcome is the occurrence of reoperations of any cause within 2 years from the index surgery. The expected reoperation rate in the non-robotic group is likely to be higher than 3-5% over a 2-year period [9–11], and may in the robotic-assisted group be 1% or less [12]. A difference of 2 percentage points or greater is considered clinically meaningful. Power analyses (80% power, α 0.05) have been made in two scenarios, with reoperation rates of 3% vs 1%, or 5% vs 3%. We estimate a ratio of 1:6 for robotic-assisted surgery vs navigation-assisted or free hand surgeries.

Comparing 3% and 1% reoperation rates, 420 robotic-assisted surgery patients and 2,520 non-robotic surgery patients are needed (yielding a total sample size of 2,940 patients). In case reoperation rates are 5% and 3%, 866 robotic-assisted surgery patients and 5,196 non-robotic surgery patients are needed (yielding a total sample size of 6,062 patients). An increased proportion of robotic-assisted surgeries or a larger difference in reoperation rates will decrease the total sample size.

An estimated 1800 patients per year are treated with pedicle screw instrumentation at the hospitals, totaling 7,200 patients in 4 years. If we after 4 years deem that the sample size will not be reached in a reasonable time frame, the study will be stopped.

No patients will be lost to follow-up, as outcomes will be ascertained through linkage with national quality, health and surgical registries, requiring no active participation from patients or clinical teams beyond standard registration. If a patient moves abroad before the 2-year period has come to an end, their existing data will be used.

To reduce confounding by indication in this non-randomized design, we will apply both propensity score matching (PSM) and inverse probability weighting (IPW). The propensity score will be estimated using logistic regression, incorporating relevant baseline covariates including age, sex, BMI, smoking status, diagnosis, number of levels fused, revision status, surgical approach (minimally invasive vs. open), interbody device use, and fixed effects for hospital site.

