Patient reported outcomes will be collected through the Swedish Spine Register (Swespine) and the Swedish Fracture Register (SFR). Response rates at 1 year is around 75-80%. Response rates in the SFR are lower. The majority of patients will be registered in Swespine (only fracture patients are registered in the SFR). Depending on diagnoses different questionnaires are used. The only questionnaires in Swespine and SFR that are distributed irrespective of diagnoses are EQ-VAS running from 0 (worst) to 100 (best possible health) and EQ-5D. Other questionnaires are Oswestry Disability Index (ODI), Scoliosis Research Society-22revised (SRS-22r), Early Onset Scoliosis Questionnaire-24 (EOSQ-24) and Short Musculoskeletal Function Assessment (SMFA), but are only answered by subpopulations. Several studies indicate that 2 year data does not result in additional information compared to 1 year data, so our primary analysis will use 1 year data, which are available in both Swespine and SFR.

Continuous outcome analysis

EQ-VAS will be analyzed as a continuous variable. We consider a 5-point difference between groups as clinically relevant at the group level, corresponding to a small-to-moderate effect size (Cohen's d appr. 0.25), with an expected standard deviation of 20 points, power 80% and α

0.05. The minimum required number of answering patients in the robotic-assisted group would be 147 and in the non-robotic-assisted group 882. We will exceed this number and achieve a quite reliable estimate if all patients are included in this analysis, also when considering that 30%-40% may not respond to questionnaires in Swespine and SFR.

PASS (Patient Acceptable Symptom State)

We will report the proportion of patients reaching a Patient Acceptable Symptom State (PASS), defined as EQ-VAS ≥ 75 for elective cases and ≥ 65 for non-elective cases. A PASS threshold of 10 percentage point difference in the proportion achieving PASS is considered meaningful. The minimum required number of answering patients in the robotic-assisted group would be 226 and in the non-robotic-assisted group 1,356 if power is 80% and α 0.05. We expect the sample size to provide sufficient power to detect any difference.

15. Recruitment

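### The PASS paragraph claims power for any difference, but only a 10-percentage-point difference was sized; the sentence is wrong as written, though the defect is minor

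*Protocol*

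**What the plan says.** The Protocol, section 14, defines PASS by EQ-VAS cut-offs and sets the effect of interest: "A PASS threshold of 10 percentage point difference in the proportion achieving PASS is considered meaningful". It then gives the size: "The minimum required number of answering patients in the robotic-assisted group would be 226". The matching figure for controls is 1,356, with 80% power and a significance level of 0.05. The paragraph closes with "We expect the sample size to provide sufficient power to detect any difference". It states no PASS rate for either group and sizes no difference other than 10 points.

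The EQ-VAS paragraph just above supplies the expected non-response: its required number will be exceeded "also when considering that 30%-40% may not respond to questionnaires in Swespine and SFR". The cohort sizes come from Substudy 3. In the smaller scenario, "420 robotic-assisted surgery patients and 2,520 non-robotic surgery patients are needed"; the larger needs 866 and 5,196. Four-year accrual is put at 7,200 patients, and the assumed ratio is 1:6.

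**The concern.** Power exists only in relation to a stated difference, and no finite sample has adequate power for every difference. The sentence therefore claims a property that the design cannot have, directly after a calculation made for one specific difference.

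The protocol is more careful elsewhere in section 14. The propensity-score text ties its power claim to the effect size fixed in advance, and the text on rare complications admits that small differences are out of reach. The PASS sentence carries no such limit.

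What is at stake is the reading of a non-significant result. Taken literally, the sentence would let someone present a null PASS comparison as adequately powered evidence that the groups do not differ. At the smaller cohort size, a true 5-point difference would be missed about two times in three.

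**Working it through.** **Inputs.** Target difference 10 points; 226 and 1,356 responders; 80% power and α 0.05 (section 14, PASS). The PASS paragraph does not state sidedness. I take two-sided, as in Substudy 1 ("Using a two-sided alpha of 0.05, 80% power, and a 1:6 group ratio"). Cohorts are 420/2,520 and 866/5,196, plus 7,200 over four years, which at 1:6 is 7,200/7 ≈ 1,029 robotic (section 14, Substudy 3). Response is 60–70%, from the stated 30–40% non-response. The PASS rate is not printed; 50% is assumed and varied below.

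**Step 1: reproduce the stated size.** Arcsine formula: n₁ = (1.960 + 0.842)² × (1 + 1/6) / h², with h = 2·arcsin√p₁ − 2·arcsin√p₂.

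- For 60% against 50%, h = 0.2014 and n₁ = 7.849 × 1.1667 / 0.04055 = 225.8, so 226, and 6 × 226 = 1,356.
- The pooled-variance formula gives 227.
- A one-sided test gives 179 and a continuity correction 238; neither matches.
- 40% against 50% has the same h, so the printed figures point to a rate near 50% but do not identify it. 70% against 60% would need 208.

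**Step 2: expected responders.** Multiply each cohort by 0.6 and 0.7. For example, 420 × 0.6 = 252 and 2,520 × 0.6 = 1,512.

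**Step 3: detectable difference and power.** With s = √(1/n₁ + 1/n₂), power = Φ(h/s − 1.960). From a 50% rate, h = arcsin(2δ), so the difference detectable with 80% power is δ = 0.5 × sin(2.8016 × s).

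Worked case, 252/1,512: s = 0.0680, so δ = 0.5 × sin(0.1906) = 0.0947, or 9.5 points. For 5 points h = 0.1002, so power = Φ(0.1002/0.0680 − 1.960) = 31%.

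| Cohort | Responders, robotic / non-robotic | Detectable at 80% power | Power, 3 points | Power, 5 points | Power, 10 points |
|---|---|---|---|---|---|
| 2,940 | 252/1,512 to 294/1,764 | 9.5 to 8.8 points | 14–16% | 31–36% | 84–89% |
| 6,062 | 520/3,118 to 606/3,637 | 6.6 to 6.1 points | 24–28% | 56–63% | about 99% |
| 7,200 | 617/3,703 to 720/4,320 | 6.1 to 5.6 points | 28–32% | 63–70% | over 99% |

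**Step 4: sensitivity.**

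- *PASS rate.* With control rates of 50% to 70%, the detectable difference is 9.5 to 8.4 points at 252 robotic responders and 5.6 to 5.1 at 720.
- *Response.* Even if every patient answered, it would be about 7.4 points at 420 robotic patients, 5.1 at 866 and 4.7 at 1,029 (50% rate).
- *Numbers needed.* At 1:6 and a 50% rate, the pooled formula needs 914 robotic responders for 5 points, 5,721 for 2 points and 22,891 for 1 point. At 70% response, 914 responders means 914/0.7 ≈ 1,306 robotic patients, above the 1,029 that four years would supply at 1:6.
- *Matching.* If PASS were analysed after 1:2 matching and 252 robotic responders were matched to 504, s = √(1/252 + 1/504) = 0.0772. Power for 10 points is then Φ(0.2014/0.0772 − 1.960) ≈ 74%. The protocol describes this matching for Substudy 3 and does not say that it applies to PASS.

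**The case against.** The strongest reply is that the sentence is loose, not false. It follows a stated meaningful difference and a minimum number of responders, just as the EQ-VAS paragraph does, so the authors may have meant any difference of that meaningful size. On that reading it is correct for an unadjusted comparison: expected responders exceed 226/1,356 and power for 10 points is at least 84%. The differences likely to be missed, 5 points or less, lie below what the protocol calls meaningful. PASS is also a secondary outcome.

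Much of this stands and limits the weight of the point. The benign reading, however, needs a qualifier that the text does not contain, and the same section does qualify its power claims elsewhere.

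A reader might infer more than the documents support:

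- *That the PASS sample size is miscalculated.* It is not; 226/1,356 reproduces.
- *That the study cannot detect anything below 10 points.* The planned cohorts exceed the minimum, so differences of roughly 6 to 9.5 points are within reach, depending on which cohort is realised.
- *That a null PASS result will be declared to show no difference.* The protocol has no rule for interpreting one, no equivalence claim and no decision that depends on PASS. It could be misread; nothing says that it will be.

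**Conclusion.** The claim of power for any difference is wrong as written and should be corrected, as a minor point of wording. The sizing supports a 10-point difference. At an assumed 50% PASS rate and 60–70% response, the foreseen cohorts extend that to about 8.8–9.5, 6.1–6.6 or 5.6–6.1 points, and power for 5 points stays at or below about 70% even at full four-year accrual.

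These figures assume a two-sided 5% test, a 1:6 split, and an unadjusted comparison in which all responders are analysed. The conclusion does not depend on the 50% rate: across control rates of 50–70%, power for 5 points with 720 robotic responders is 70–79%, and for 2 points 17–19%. Covariate adjustment or matching could change the exact values, and discarding controls by matching would lower them.

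**What to change.** In the closing PASS sentence, replace the reference to any difference with a 10-percentage-point difference. Have the authors state the PASS rate they assumed; it should come from them, since the printed numbers do not identify it. Then give the smallest difference detectable with 80% power at the expected number of responders. If their rate was 50%, that is 8.8–9.5 points at 2,940 patients, 6.1–6.6 at 6,062 and 5.6–6.1 at 7,200. Add that these values hold for an unadjusted comparison of all responders, and that matching would lower the power (about 74% for 10 points if 252 robotic responders were matched 1:2).

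The cost is a protocol wording change. No patients, data or analyses are affected. The downside is that the stated power becomes less favourable.

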Robotic-assisted surgery (RAS) represents a further step in this evolution. These systems, which use a navigated robotic arm to assist screw placement, aim to enhance accuracy and reduce variability—which may be especially beneficial for less experienced surgeons. RAS may also streamline intraoperative workflow and support minimally invasive approaches. While early results are promising, there remains limited evidence on the broader clinical benefits, especially during the early learning phase of implementation [4]. Robotic-assisted spine surgery is not sanctioned by the Swedish Association of Authorities and Regions, unless performed in clinical trials.

This study aims to evaluate the clinical introduction of robotic systems in spine surgery, focusing on their impact on reoperations, screw placement accuracy, complications, outcome, and intraoperative workflow.

7. Objectives

This study has three main objectives, analysed in three different substudies: To study screw placement accuracy, learning curve, and reoperations.

Secondary Objectives: To assess complications, patient-reported outcomes, length of stay, surgical time, and cost-effectiveness.

8. Trial Design

Multicenter, non-randomized observational cohort study with consecutive patient inclusion.

9. Study Setting

All hospitals in Sweden performing spinal surgery will participate.

10. Eligibility Criteria

Inclusion Criteria:

- Treatment with pedicle screws in the cervical, thoracic, lumbar spine and/or sacrum.
- All ages and spinal diagnoses

Exclusion Criteria:

- Treatment without pedicle screws

Consent

-All patients will be treated according to each hospital's routine. Patient consent will therefore not be needed.

11. Interventions

Experimental Group: Robotic-assisted pedicle screw insertion using available equipment. Currently available systems are Brainlab Cirq and Mazor Robotics, but others systems may be used.

Control Group: Patients undergoing non-robotic-assisted (freehand or navigation-assisted) pedicle screw placement.

12. Outcomes

Primary objectives and outcomes

Substudy 1 primary outcome - Screw placement accuracy (binary per-patient outcome)

- Proportion of patients in which at least one screw is not accurately placed.

Substudy 2 primary outcome- Learning curve (surgical time)

-To evaluate when time in surgery is no longer decreasing in robotic-assisted surgery.

Substudy 3 primary outcome - Reoperation rate at 2 years

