-The primary outcome is the occurrence of reoperations of any cause within 2 years from the index surgery in patients undergoing robotic-assisted surgery compared to non-robotic-assisted (navigation-assisted or free hand) surgery.

Secondary Outcomes

- Intraoperative (screw placement precision, including comparisons preoperative and postoperative positioning for screws and rods, surgical time; skin-to-skin as well as wheel-in wheel-out time, estimated patient radiation exposure, intraoperative bleeding)
- Postoperative outcomes (length of stay, patient-reported outcome measures (PROMs), time to return to work)
- Cost-effectiveness and procedural resource use
- Complications (care related infections, thrombosis, emboli, cardiovascular, mortality)

Table 1

Table over data collection and source.

	Radiographic data	Reoperations	Intraoperative metrics	Postoperative outcomes; complications, PROMs
Data source	PACS	SPOR, Swespine, NPR	SPOR/Surg planning program/Electronic health records	Swespine, SFR, SPOR, Electronic health records
Data origin	Radiology department	Surgeon, Anesthesiologist, Hospital	Surgeon/Anesthesiologist	Patient
Need for separate assessment	Yes, radiographic assessment by the investigators	No	No	No
Time points for data collection	Preoperative, intraoperative, postoperative, up to 2 years	Postoperative, within 2 years	Intraoperative	Preop and up to 2 years postoperative

[figure not shown]
Swespine: Swedish Spine Register

SFR: Swedish Fracture Register

SPOR: Swedish PeriOperative Register

13. Participant Timeline

Figure 1. Participant timeline. Data will be collected up to 5 years postoperative.

14. Sample size

Substudy 1- Primary outcome- Screw placement accuracy (binary per-patient outcome)

Accurate screw placement is defined as a pedicle screw that remains entirely within the cortical boundary of the pedicle, or with up to 2 mm breach of the pedicle wall (corresponds to Gertzbein-Robbins Grade A and B) [5]. To evaluate screw placement accuracy, we will define a binary per-patient outcome: whether at least one screw is not accurately placed.

Based on previous literature, robotic-assisted systems may achieve clinically acceptable accuracy per screw (Gertzbein-Robbins Grade A and B) of approximately 97%, while navigated systems achieve approximately 93% [6], and freehand 84-90% [7, 8].

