Patients will be included consecutively at each site during the enrollment window which is planned to be four years (2025–2029). Currently robotic-assisted spine surgery is available in two hospitals (Umeå and Örebro), with a third hospital waiting for their equipment to be installed (Uppsala). If other hospitals install robotic-assisted surgery during the study period this will just result in more patients involved in the robotic-assisted arm of the trial, which would result in a potentially faster inclusion of the needed amount of patients. We still believe that during the study period more patients will be operated with non-robotic-assisted methods than with robotic-assisted methods.

16–17. Allocation and blinding

No randomization or blinding will be performed. If a planned robotic-assisted surgery is abandoned after the start of surgery, the patient will be included in the robotic-assisted group (i.e. intention to treat principle).

18. Data collection methods

Data will be collected through national registries (Swespine, the Swedish Fracture Register, the Swedish PeriOperative Register, hospital systems (electronic health records, surgical planning software, Picture Archiving and Communication System; PACS and others). PROMs will be recorded preoperatively, and at follow-ups (Swespine: 1, 2 and 5 years; the Swedish Fracture Register: 1 year). Images will be retrieved using standardized CT protocols and assessment will be made by at least two researchers independently.

19. Data management

Data will be collected and managed in compliance with GDPR. Regular validation and updates will occur every 6–12 months. Final datasets will be stored at Uppsala University for a minimum of 15 years.

20. Statistical methods

Statistical analysis will compare outcomes using appropriate parametric or non-parametric tests,

including survival methods. Baseline characteristics will be adjusted for using multivariable models. Adjustment variables include age, diagnosis, comorbidities, previous spine surgery, number of levels, number of screws, robotic system type, use of navigation or free-hand surgery and hospital.

Analysis is currently planned to be performed in R. Interim analyses will be performed when half of the patients have been included. Sensitivity analyses will be performed as described earlier.

21. Data monitoring

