If funding is available a formal Data Monitoring Committee will be appointed. All data are collected within the regular health care system which means that the data is subject to regular clinical monitoring as part of standard practice. Reporting of deviations (clinical practice or complications) will be done within regular hospital systems.

22. Harms

Harms will be tracked via registry data and clinical records. These include infections, reoperations, and other adverse events, including mortality.

23. Auditing

Study sites may be subject to independent audits by the hospital, external parts contracted by the hospital or governmental agencies. Records will be maintained in compliance with Good Clinical Practice.

24. Ethics Approval

Ethical approval will be obtained from the Swedish National Ethical Review Authority prior to initiation.

25. Protocol Amendments

All protocol changes will be documented. If protocol changes require submission for ethical approval this will be done prior to implementation, except in urgent safety situations.

26. Consent and confidentiality

Informed consent is not required since all interventions are standard of care. After data extraction and before analyses, all data will be pseudonymized and handled in accordance with national privacy legislation.

27. Declaration of interests

[name] has received lecture fees from DePuySynthes, Johnson and Johnson Medtech (to himself). [name] has received lecture fees from DePuySynthes, Johnson and Johnson Medtech (to himself). [name] has received teaching honoraria and a research grant from Medtronic. All other investigators and collaborators declare they have no conflict of interest.

28. Access to data

The research group (investigators and collaborators) will have access to the final dataset.

29. Ancillary and post-trial care

No specific post-trial care beyond standard clinical and national quality and health register-based follow-up is planned.

30. Dissemination policy

The results will be submitted for peer-reviewed publication and presented at scientific conferences. Summary findings will be posted in public trial registries.

31. Use of generative AI

Generative AI (Chat GPT 4o) has been used for assistance in coding the preliminary power analyses and for grammar correction. Power analyses has then independently been recalculated by statistician [name] at “Statistikakademin”, Uppsala, Sweden.

Figure 2. Study timeline. Years are indicated.

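### The Protocol rules out all blinding and has investigators grade screw accuracy at a 2 mm cut-off, so the Substudy 1 primary outcome is open to reader bias that masked CT reading would reduce

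*Protocol*

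**What the plan says.** - **Blinding.** Protocol sections 16–17: "No randomization or blinding will be performed". No exception is made for outcome assessment.
- **Who reads.** Table 1 in section 12 asks whether each data type needs separate assessment. Only radiographic data do: "Yes, radiographic assessment by the investigators". Section 18 adds that "assessment will be made by at least two researchers independently", without saying that the readers are masked.
- **What is judged.** Section 14 counts a screw as accurate if it lies wholly within the pedicle cortex "or with up to 2 mm breach of the pedicle wall" (Gertzbein-Robbins A or B).
- **Outcome.** Section 12 gives the Substudy 1 primary outcome as "Proportion of patients in which at least one screw is not accurately placed".
- **Nearest safeguard.** Section 26: "After data extraction and before analyses, all data will be pseudonymized". It does not say that treatment group is hidden or that this step precedes the image reading.
- **Related reading task.** In section 14, screw precision is measured in robotic cases only, by overlaying the surgical plan on the intra- or postoperative CT.

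**The concern.** Surgeons cannot be blinded here, but CT readers can be, because the images are retrieved from PACS and read as a separate task. Whether a breach is just under or just over 2 mm is a judgement, and the outcome passes that judgement straight to the patient level: one screw across the line makes the patient an event. Section 14 expects most patients to have more than four screws, which gives more chances for such a call.

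Independent double reading reduces random error, but not an expectation that both readers hold. The propensity score methods and covariate adjustment in sections 14 and 20 deal with confounding, not with an outcome graded differently by group. A larger sample does not help either. In a non-randomised comparison meant to inform whether robotic placement should be used, this is a source of doubt that the design could largely avoid.

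**Working it through.** **Inputs from Protocol section 14.** Per-screw accuracy is 97% robotic and 93% navigated (84–90% freehand). It assumes 4 screws per patient, two-sided alpha 0.05, 80% power, a 1:6 ratio, and 71 vs 426 patients, with the robotic group raised to 75 (501 in total).

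**Step 1: reproduce the plan's figures.** With screws treated as independent, the patient-level rate is 1 − a⁴, where a is per-screw accuracy.
- Robotic: 1 − 0.97⁴ = 11.5% (stated as 12%).
- Non-robotic: 1 − 0.93⁴ = 25.2% (stated as 25%).
- Difference: 13.7 points.

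The arcsine formula for two proportions, with these unrounded rates, a ratio of 6 and 80% power, gives 71 and 426. The stated sample size reproduces exactly, and nothing below depends on an error in it.

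**Step 2: regrading when the planned difference is real.** Let f be the share of inaccurate robotic screws that readers call accurate, with controls unchanged. The Protocol gives no value for f, so 10% to 30% is an assumed range. The robotic rate becomes 1 − (1 − 0.03(1 − f))⁴.

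| f | Robotic | Control | Difference |
|---|---|---|---|
| 0 | 11.5% | 25.2% | 13.7 points |
| 10% | 1 − 0.973⁴ = 10.4% | 25.2% | 14.8 points |
| 20% | 1 − 0.976⁴ = 9.3% | 25.2% | 15.9 points |
| 30% | 1 − 0.979⁴ = 8.1% | 25.2% | 17.1 points |

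**Step 3: regrading when there is no true difference.** Both groups have 7% inaccurate screws (25.2% of patients). The robotic rate as read is p₁ = 1 − (1 − 0.07(1 − f))⁴; the control rate is p₂ = 25.2%. The chance of a significant result at 75 vs 426 uses the normal approximation, with the pooled standard error for the critical value and the unpooled one for the sampling distribution.

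| f | p₁ | Spurious difference | Chance of p < 0.05 |
|---|---|---|---|
| 0 | 25.2% | 0 | 5.0% |
| 10% | 22.9% | 2.3 points | 6.5% |
| 20% | 20.6% | 4.6 points | 12.4% |
| 30% | 18.2% | 7.0 points | 23.8% |

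Example for f = 30%:
- The pooled rate is (75 × 0.1821 + 426 × 0.2519)/501 = 0.2415.
- The pooled standard error is 0.0536, so the critical difference is 1.96 × 0.0536 = 0.105.
- The unpooled standard error is 0.0493.
- (−0.105 + 0.070)/0.0493 ≈ −0.71, which has a tail probability of about 0.238. The other tail is negligible.

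**Step 4: an upper bound.** To produce the whole planned contrast (25% vs 12%) from nothing, the robotic per-screw inaccuracy as read would have to be 1 − 0.88^(1/4) = 3.1% instead of 7%. That means f = 1 − 0.0315/0.07 ≈ 55%.

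**The case against.** The blinding sentence stands under a heading on allocation and is followed by a rule on abandoned robotic procedures. It could be meant for treatment only, with image reading left to a manual or analysis plan not shown here. Against this, the wording has no exception, and any later document that masked the readers would contradict it as it stands.

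The Protocol also has real safeguards: a published grading scale, standardised CT protocols and two independent readers. They limit error in general, but none is stated to hide the group.

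Three stronger readings are tempting and are not supported:
- **That teams from the robot centres grade their own cases.** A reader might infer this, but the Protocol says only investigators and researchers. It does not give their hospitals, and all Swedish hospitals performing spine surgery take part.
- **That a trivial shift inflates the effect by half.** Moving one screw in 100 each way (97% to 98% and 93% to 92%) gives 1 − 0.98⁴ = 7.8% vs 1 − 0.92⁴ = 28.4%, or 20.6 points. But this regrades a third of the inaccurate robotic screws (3% to 2%) and raises the control inaccuracy by a seventh (7% to 8%) at once. It is one scenario, and not a small one.
- **That masking removes the bias for almost nothing.** Scan type or timing may reveal the group. The study is unfunded, and 501 patients with at least 4 screws means at least 501 × 4 = 2,004 screws to handle. The Protocol gives no cost figure.

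**Conclusion.** The point holds for Substudy 1. The Protocol expressly rules out blinding, gives a judgement-based primary outcome to investigators to grade, and states nothing that hides the group from them. Because the stated rule itself needs changing, this is not a detail that can be left to an analysis plan.

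The size and direction of any bias are unproven. Over the assumed 10% to 30% range of one-sided regrading, the effect goes from minor (about 1 point added to the planned difference, 6.5% false positives) to serious (about 3.4 points added, 24% false positives). These figures assume 4 independent screws per patient, controls read correctly and an unadjusted comparison. Regrading in the opposite direction would bias against the robot.

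Reoperations in Substudy 3 come from registries and need no separate assessment under Table 1, so this point does not reach them. The change is worth making before accuracy reading starts.

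**What to change.** Amend sections 16–18 to state that:
- treatment is not blinded for surgeons or patients;
- CT images for accuracy grading are stripped of treatment group, hospital, surgeon and date, and put in mixed random order;
- the independent readers already planned grade them masked to group;
- accuracy grading is completed before, and kept separate from, the plan-overlay precision measurement, which exists only for robotic cases and so discloses the group;
- cases are assigned among the existing investigators so that none grades their own where feasible. Fixing the same two readers for every image could fail if either of them operates on study patients.

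The cost is de-labelling, random ordering and a reading log. The sample size does not change. Scan type or timing may still unmask some cases, so the report should claim reduced reader bias, not its absence.
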